6. GENERAL STATISTICAL CONSIDERATIONS

6.1. General Principles

This is a proof of concept double-blind placebo controlled randomized trial testing a superiority hypothesis where interventions with a two-sided p-value $< .20$ will be declared promising and will be considered statistically significant if the final two-sided p-value is $< .05$. These data will be summarized by treatment (intervention name versus placebo) and when appropriate by baseline ordinal score. Additionally, data will be described according to the appropriate summary statistics, e.g.

- Percentages/proportions/odds ratios for categorical data. For tabular summaries of percentages/proportions, the denominator (e.g., number of subjects in the specified population) will be displayed.
- Means, standard deviation, median, and/or range for continuous data, median and confidence intervals for time-to-event data.

Confidence intervals will be generated; 95% and 80% confidence intervals will be generated for primary and key secondary outcomes. For hazard ratio and odds ratio estimates, Wald confidence intervals will be used. For confidence intervals of proportions for other efficacy and safety outcomes, Blaker confidence intervals will be used.

In general, all tables will have corresponding listings of data presented unless noted otherwise.

When calculating treatment effects (e.g., differences, hazard ratios, odds ratios) from regression modelling, placebo will be used as the reference group. Subjects on interventions will only be compared to control subjects who could potentially have been randomized to that intervention (i.e., they met eligibility criteria for the intervention and are at a site where the intervention was enrolling at the time of the subject's randomization). Analyses of newly added arm(s) will be performed comparing concurrently enrolled control subjects. For any modeling that uses covariates defined in Section 6.4, the category listed last for each variable in that section will be used as the control group for the interaction analysis and covariate-adjusted analyses.

For the time-to-event analyses, the following SAS pseudocode will be used to generate stratum-specific median time to event estimates and confidence intervals and stratum-specific Kaplan-Meier curves.

```
proc lifetest data=dataset plots=(s);
  time timevariable * censorvariable(1);
  test treatmentvariable;
run;
```

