In this approach, `timevariable` represents the time until the event in question (e.g., recovery), `censorvariable` represents the censoring variable (e.g., 0= event observed, 1= event did not occur at the time of withdrawal, discharge, lost-to-followup, etc), and `treatmentvariable` represents the intervention (e.g., 0= remdesivir + placebo, 1= remdesivir + new treatment).

To perform a Cox proportional hazards analysis and generate the treatment hazard ratio along with its Wald confidence interval and p-value from the score test after adjusting for other covariates, the following SAS pseudocode will be used.

```
proc phreg data=dataset;
  class treatmentvariable(ref=placebolabel) othercovariates;
  model timevariable * censorvariable(1) = treatmentvariable othercovariates /
  ties=efron;
  hazardratio treatmentvariable / diff=ref cl=wald;
```

```
ods output hazardratios = hrest globaltest=pvalue;
run;
```

To assess the assumption of proportional hazards for Cox models, Kaplan-Meier curves for each treatment arm will be produced (PH assumption supported if curves do not cross). Restricted mean survival time along with its 95% CI will be reported to assess whether the results change if the PH assumption is not satisfied.

Proportional Odds analysis without MI:

The following SAS pseudocode will be used to perform the proportional odds analysis with treatment, baseline ordinal score and baseline steroid use as covariates to generate the treatment odds ratio, p-value, and predicted probabilities of the ordinal scale levels by treatment and ordinal score using complete data

```
proc logistic data=dataset out=imp_parms plots(only)=effect(x= ordscore_d8
  sliceby =baseordscorevar*trtvar individual connect);
  class baseordscorevar (param=ref ref=5) basesteroidusevar (param=ref ref=no
steroid use) trtvar (param=ref ref=placebolabel);
  model ordscore_d8 = trtvar baseordscorevar basesteroidusevar;
  oddsratio trtvar;
  ods output oddsratioswald = orest;
run;
```

For the endpoints analyzed by proportional odds, odds ratios between the binary progression strata will be computed, to support data understanding. For example, odds ratio, confidence intervals from logistic regression will be reported for treatment effect for the binary endpoint of OS= 1-7 vs 8, then OS= 1-6 vs 7-8, etc. Similar odds ratios across these 7 2x2 tables will support the proportional odds assumption.

95% Blaker confidence intervals for proportions/percentages:

```
proc freq;

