  by analysisvariable;
  table trtvar/alpha=0.05 binomial (cl=blaker);
  ods output binomialcls=outputdsn2;
run;
```

Risk differences and 95% CI Using Miettinen-Nurminen:

```
proc freq data = analysis;tables trtvar*aval/ out=mncidat;run;

proc sort data=mncidat;by trtvar;run;

ods select PdiffCLs;
ods output PdiffCLs=mnci_d5v;
proc freq data=mncidat order=data;
  tables trtvar*aval /riskdiff (CL=( MN ));
  weight count;
run;
```

Odds ratios from logistic regression without MI:

```
proc logistic data=dataset out=imp_parms;
  class baseordscorevar (param=ref ref=5) basesteroidusevar (param=ref ref=no
steroid use) trtvar (param=ref ref=placebolabel);
  model aval (event='Yes') = trtvar baseordscorevar basesteroidusevar;
  oddsratio trtvar;
  ods output oddsratioswald = orest;
run;
```

Risk differences from logistic regression using the approach described in Ge et. Al [2]:

```
proc logistic data = dataset outmodel=pout;
  class trtvar ;
  model surv(event='1') = trtvar othercovariates ;
run;

*Create dataset tempa to contain all subjects and assign them the active treatment and
dataset tempg which include all subjects assigned the placebo treatment;

proc logistic inmodel=pout;
  score data = tempa out=preda(keep=id P_a rename= (P_1=P_a)) ;
run;

proc logistic inmodel=pout;
  score data = tempg out=predp(keep=id P_1 rename= (P_1=P_p)) ;
run;

proc sort data=pred1;by subjectid;run;
proc sort data=pred2;by subjectid;run;

*Combine to obtain risk differences in probabilities for each subject;

data comb;
  merge predp predp;
  by subjectid;
  diff=P_a-P_p;
run;

proc means data=comb;var diff;run;
```

To obtain the CI for the risk difference, use bootstrap with the following steps:

1. Sample with replacement from the dataset.
2. Obtain risk difference estimate for each bootstrap sample.
3. Repeat this step the above step 1000 times and use the 25th and 975th values from the sorted list of the 1000 risk estimates as the limits for the 95% CI for the risk difference. The risk difference estimate from bootstrap can be estimated as the mean of the 1000 risk estimates and should be equal to the risk difference obtained prior to performing bootstrap.

All statistical analyses and summaries will be performed on the mITT, ITT, and/or Safety populations. In general, the efficacy analysis will be performed mITT population and the safety analysis will be conducted on the Safety population. Any exceptions will be stated in the stage-specific appendix.

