Non-invasive ventilation/high flow-oxygen days or worse will be defined as the number of days where the ordinal score is > 5 up to and including Study Day 29. The total number of days will be the sum of all reported days, regardless of whether the days occur consecutively or in disjoint intervals. For planned gaps between study days, the day of the qualifying Study Day and the days to the next planned Study Day will be included in the total number of days. The Post-Discharge Supplemental Oxygen CRF questions regarding days of non-invasive ventilation or high-flow oxygen will be used for any time period the subject is not hospitalized at the study hospital. See Section 6.5 for the plan for handling subjects who do not have data through Study Day 29 or die prior to Study Day 29.

Duration of non-invasive ventilation/high flow oxygen days or worse will be summarized in a table using medians and quartiles by treatment (Table 37). Bee swarm plots of non-invasive ventilation/high flow oxygen days by treatment will be generated (Figure 20).

The incidence and duration of new Non-Invasive Ventilation/High-Flow Oxygen use or worse will be analyzed by treatment (Table 40). The numerator will include only subjects in category 5 or below at enrollment who change to a category 6, 7, or 8. The denominator will only include subjects with an actual baseline ordinal score of 5 or below at enrollment. The number of subjects reporting new use of Non-Invasive Ventilation/High-Flow Oxygen and the incidence rate along with 95% and 80% CIs estimated using the Blaker method will be reported.

Refer to Table 6 for a list of covariates and subgroup analyses for this endpoint. Refer to Table 7 for imputation methods to be applied to this endpoint.

Invasive Mechanical Ventilation/ECMO

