Ventilator / ECMO days will be defined as the number of days where the ordinal score > 6 up to and including Study Day 29. The total number of days will be the sum of all reported days, regardless of whether the days occur consecutively or in disjoint intervals. For planned gaps between study days, the day of the qualifying Study Day and the days to the next planned Study Day will be included in the total number of days. The Post-Discharge Supplemental Oxygen CRF questions regarding days of ECMO or invasive ventilation will be used for any time period the subject is not hospitalized at the study hospital. See Section 6.5 for the plan for handling subjects who do not have data through Study Day 29 or die prior to Study Day 29.

Duration of Invasive Mechanical Ventilation/ECMO days will be summarized in a table using medians and quartiles by treatment (Table 38). Bee swarm plots of Invasive Mechanical Ventilation/ECMO days, and days hospitalized by treatment will be generated (Figure 21).

The incidence of new Invasive Mechanical Ventilation/ECMO use will be analyzed by treatment (Table 41). The numerator will only include subjects in category 6 or below at enrollment who change to a category 7 or 8. The denominator will include subjects with a baseline ordinal score of 6 or below. The number of subjects reporting new use of Invasive Mechanical Ventilation/ECMO and the incidence rate along with 95% and 80% CIs estimated using the Blaker method will be reported.

Refer to Table 6 for a list of covariates and subgroup analyses for this endpoint. Refer to Table 7 for imputation methods to be applied to this endpoint.

Proportion of Subjects Alive and Without Respiratory Failure at Study Day 29

The proportion of subjects alive and without respiratory failure at Study Day 29 will be defined as the proportion of subjects with an ordinal score < 7 at any time between Day 26 through Day 32 (Visit window for Study Day 29 Visit). The proportion of subjects with respiratory Failure or death at Day 29 will also be provided. These proportions will be presented by treatment along with 95% and 80% Blaker CIs. Treatment differences will be evaluated using a logistic regression and the p-value will be presented (Table 31).

Refer to Table 6 for a list of covariates and subgroup analyses for this endpoint. Refer to Table 7 for imputation methods to be applied to this endpoint.

Time to Mechanical Ventilation or Death up to and Including Day 29

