Table 40: Incidence of Secondary Outcomes – Non-Invasive Ventilation/High Flow Oxygen Free Days or Worse through Day 29 — mITT Population

Outcomes	Treatment	Population at Risk ^a		New Cases ^b		Incidence Rate		
		n	%	n	%	Estimate ^c	95% CI ^d	80% CI ^d
Primary Analysis	Treatment A (N=X)	x	x.x	x	x.x	x.xxx	x.xxx, x.xxx	x.xxx, x.xxx
	Treatment B (N=X)	x	x.x	x	x.x	x.xxx	x.xxx, x.xxx	x.xxx, x.xxx
Subgroup Analysis								
Repeat for each sensitivity and subgroup category as detailed in Table 6 and Table 7.								
N=Number of subjects in modified intent-to-treat (mITT) population. n= Number of unique subjects that satisfies the row criteria. ^a Population at risk is defined as all subjects with a baseline ordinal score of 5 or below. ^b New cases are defined as subjects with a baseline ordinal score of 5 or below that progress to an ordinal score of 6, 7, or 8. ^c The incidence rate is the proportion of the population at risk that have new cases. ^d Confidence intervals for the incidence rate estimated using Blaker method.								

Table 41: Incidence of Secondary Outcomes – Ventilator/ECMO Days or Worse through Day 29 — mITT Population

Outcomes	Treatment	Population at Risk ^a		New Cases ^b		Incidence Rate		
		n	%	n	%	Estimate ^c	95% CI ^d	80% CI ^d
Primary Analysis	Treatment A (N=X)	x	x.x	x	x.x	x.xxx	x.xxx, x.xxx	x.xxx, x.xxx
	Treatment B (N=X)	x	x.x	x	x.x	x.xxx	x.xxx, x.xxx	x.xxx, x.xxx
Subgroup Analysis								
Repeat for each sensitivity and subgroup category as detailed in Table 6 and Table 7.								
N=Number of subjects in modified intent-to-treat (mITT) population. n= Number of unique subjects that satisfies the row criteria. ^a Population at risk is defined as all subjects with a baseline ordinal score of 6 or below. ^b New cases are defined as subjects with a baseline ordinal score of 6 or below that progress to an ordinal score of 7 or 8. ^c The incidence rate is the proportion of the population at risk that have new cases. ^d Confidence intervals for the incidence rate estimated using Blaker method.								

Table 42: Time to Mechanical Ventilation or Death through Day 29 — mITT Population with Baseline Ordinal Score of 5 or 6, CRP<150 mg/L, and age<85 years

Analysis/Subgroup	Treatment	Number of Subjects to Mechanical Ventilation or Death ^d		Median Time Until Event			Hazard Ratio			P-value ^e
		n	%	Estimate	80% CI	95% CI	Estimate	80% CI	95% CI	

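### The SAP's only Blaker code has its BY and TABLE variables reversed, so it estimates an arm share instead of the event proportion within each arm

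*SAP*

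**What the plan says.** SAP section 6.1 assigns the method: "For confidence intervals of proportions for other efficacy and safety outcomes, Blaker confidence intervals will be used". Later in that section, under the label "95% Blaker confidence intervals for proportions/percentages", it gives the only code for it: a PROC FREQ step with "by analysisvariable" as the BY statement and "table trtvar/alpha=0.05 binomial (cl=blaker" as the table request. The name `analysisvariable` is not defined anywhere, and the request names no outcome level.

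Section 8.2.2 and the table shells say what the intervals are for:

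- **Table 31**, survival without respiratory failure at Day 29: "These proportions will be presented by treatment along with 95% and 80% Blaker CIs".
- **Table 40**, new non-invasive ventilation or high-flow oxygen: the number of new users and "the incidence rate along with 95% and 80% CIs estimated using the Blaker method", among subjects with a baseline score of 5 or below.
- **Table 41**, new invasive ventilation or ECMO: "The denominator will include subjects with a baseline ordinal score of 6 or below". The shell footnote adds: "The incidence rate is the proportion of the population at risk that have new cases".

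All three shells report each arm separately, with both 95% and 80% limits.

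**The concern.** In PROC FREQ the BINOMIAL option estimates the proportion of the variable named in the table request, separately in each BY group. Here that variable is treatment. The step therefore describes how subjects divide between arms within a BY group. It does not describe how often the outcome occurs within an arm.

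The denominator is wrong as well. It becomes the subjects who share an outcome, when it should be the subjects at risk in one arm. If the step were followed literally, the estimates and limits for new non-invasive support, new invasive ventilation and Day 29 respiratory failure would belong to a different quantity.

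**Working it through.** The SAP states no Blaker figure to reproduce, so the check is on what the code computes.

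**Formulas.** Let e_P and e_A be the events among n_P placebo and n_A active subjects.

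- Required: e_P/n_P and e_A/n_A.
- Code as written, outcome as BY variable, event group: e_P/(e_P + e_A) if placebo is the first level, or e_A/(e_P + e_A) if active is.
- Code as written, no-event group: (n_P − e_P)/[(n_P − e_P) + (n_A − e_A)] with placebo first.

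With no level named, the option reports the first sorted level. The SAP's only coding example, given in section 6.1 for the treatment variable of the survival code, is 0 for placebo and 1 for active. On that coding placebo comes first.

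**Simple example (assumed counts).** Take 20/100 events on placebo and 10/100 on active.

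- Required: 20% and 10%.
- Code, event group: 20/30 = 66.7% with placebo first, or 10/30 = 33.3% with active first.
- Code, no-event group, placebo first: 80/(80 + 90) = 47.1%.

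**Example from the SAP's planning figures.** Inputs are 100 per arm (section 5); Table 4 control-arm categories 7 and 8, 24.2% + 3.5% = 27.7%; and an odds ratio of 2 (section 5). These are Day 8 figures, used only for scale, and all 100 subjects per arm are taken as at risk. Control odds are 0.277/0.723 = 0.383. Halved, they are 0.192, so the active rate is 0.192/1.192 = 16.1%. Rounded to whole subjects this gives 28 and 16 events. Blaker limits were computed numerically.

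| Quantity | Estimate | 95% limits | 80% limits |
|---|---|---|---|
| Required, placebo | 28/100 = 28.0% | 19.7 to 37.6 | 22.5 to 34.5 |
| Required, active | 16/100 = 16.0% | 9.7 to 24.3 | 11.4 to 21.5 |
| Code, event group, placebo first | 28/44 = 63.6% | 48.5 to 76.6 | not coded |
| Code, event group, active first | 16/44 = 36.4% | 23.4 to 51.5 | not coded |

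The no-event group gives 72/(72 + 84) = 46.2% with placebo first.

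**Absolute risk is lost.** With equal arms the event-group result depends only on the ratio of the two event counts.

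- 28 v 28 events: 28/56 = 50% (36.4 to 63.6), when each arm's rate is 28.0%.
- 10 v 10 events: 10/20 = 50% (29.3 to 70.7), when each arm's rate is 10.0% (5.1 to 17.2).

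**The other reading of the undefined name.** If `analysisvariable` identified the endpoint instead of its value, each BY group would contain everyone. The step would then return the allocation share, 100/200 = 50% (43.0 to 57.0). That is not an event proportion either.

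**The case against.** The strongest reply is that this is pseudocode and the plan defines the right quantity elsewhere. Section 8.2.2 gives numerators and denominators, and the shells are laid out by arm. Output with one block per outcome level could not fill them, so a programmer would probably notice. The surrounding code is also schematic: the risk-difference example in section 6.1 merges a dataset with itself and sorts datasets that it never creates. This stands, and it keeps the point minor. It does not make the step correct. No other code for the Blaker interval is given, and the Miettinen-Nurminen example in the same section crosses treatment with outcome in the usual way, so the reversal looks like a local slip.

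A second reply concerns the 80% limits. The block is labelled as the 95% version, so its alpha matches its label. That stands too: the absence of an 80% version is a gap in completeness and not an error.

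Three stronger readings are tempting but lack support:

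- A reader might infer that the code returns the share of events on active drug. It names no level, and on the SAP's coding example the reported share is placebo's.
- A reader might infer that the step would run cleanly and mislead silently. It names no dataset and has no preceding sort, and BY processing needs sorted input, so this cannot be asserted.
- A reader might infer that the reported rates will be wrong. That would require following the code against both the text and the shells.

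**Conclusion.** The code is wrong as written and should be corrected, at low priority. Under either reading of the undefined BY variable it estimates an arm share, near 50% when the arms are equal and there is no effect. It never estimates the event proportion per arm. Describing the output as the split among subjects with a given outcome assumes that `analysisvariable` is the outcome. Which arm is reported depends on sort order. The percentages above rest on assumed event counts.

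The reach is limited to the descriptive intervals in Tables 31, 40 and 41. The p-value in Table 31 comes from logistic regression, and Tables 40 and 41 contain no test. The proportional odds analysis of Day 8 status, the Cox analysis of sustained recovery, the Kaplan-Meier and logistic analyses of survival without respiratory failure, and the interim rules do not use this step.

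**What to change.** Replace the block in SAP section 6.1 as follows:

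1. Restrict the data to the at-risk population where the table needs it: baseline score 5 or below for Table 40, and 6 or below for Table 41.
2. Sort by `trtvar`.
3. Run `by trtvar; tables aval / alpha=0.05 binomial(level='Yes' cl=blaker);`. The level should match how each outcome is coded; `Yes` follows the event coding in the SAP's logistic example. For Table 31, run it for each of the two status rows.
4. Repeat with `alpha=0.20` for the 80% limits, and change the label of the block to cover both levels.

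Using `aval`, the outcome name in the neighbouring code, also removes the undefined placeholder. The cost is a few lines of pseudocode, with no change to any estimand, shell, data collection or sample size.

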6.2. Timing of Analyses

6.2.1. Interim Analyses

A Data and Safety Monitoring Board (DSMB) will monitor ongoing results to ensure subject well-being and safety as well as study integrity. The DSMB will be asked to recommend early termination or modification only when there is clear and substantial evidence of a treatment difference. Interim analyses for a given stage will be conducted after each intervention arm and the comparison control arm has approximately 50 subjects with Study Day 8 assessments. The DSMB may use the following guidelines:

- consider an arm futile at the interim evaluation if the odds ratio point estimate for the primary endpoint is <1 .
- consider an intervention arm efficacious if the p-value after 50 subjects per arm is <0.001 and OR estimate >1 .
- consider to not recommend discontinuing an arm if the p-value is <0.001 , if members judge it would be more beneficial to collect more data before announcing the results.

Any time-to-event outcomes for the interim analyses will be analyzed through Study Day 29. The efficacy boundary follows a Haybittle-Peto approach. Given that the statistical adjustment for multiplicity due to this 0.001 boundary would be very minimal, no adjustment to the final p-value will be made, in this proof of concept study.

Safety analyses will evaluate Grade 2 (drug related hypersensitivity only), 3 and 4 AE, AESIs, and SAEs by treatment arm and baseline ordinal score. Safety monitoring will be ongoing (see study protocol Section 10.1.6) and evaluate safety results weekly. The unblinded statistical team will prepare these reports by baseline ordinal score with treatment groups collapsed for review by the DSMB. The unblinded statistical team may also prepare these reports by blinded treatment arm for review by the DSMB, if requested.

The unblinded statistical team will prepare the closed reports for DSMB review and recommendations. Analyses will be presented with blinded codes for treatment arms to protect against the possibility that the DSMB report may fall into the wrong hands. A DSMB charter will further describe procedures and membership.

